Febrile neutropenia	Grade 3	Discontinue everolimus until fever resolves and grade ≤ 1 neutropenia returns. Continue everolimus interruption until PNN is $\geq 1,500/\text{mm}^3$ and fever disappears. Then resume everolimus at the lower dose level. If febrile neutropenia recurs, discontinue everolimus.
	Grade 4 (life-threatening)	Stopping everolimus
Any hematological toxicity	Requiring an interruption for a period ≥ 3 weeks	Stopping everolimus

Table1-3:

Toxicity ANEMIA (Hemoglobin decrease) NCI-CTC v4.0	Grade	Dose adjustment
Anemia	Grade 1 or 2	No change in dose
	Grade 3	Interrupt everolimus until recovery to grade ≤ 2 , then resume everolimus at the same dose. If return to grade 3, withhold everolimus until grade ≤ 2 , then resume at lower dose level. Discontinue everolimus in case of 3 ^{ième} grade 3 episode.
	Grade 4	Permanent discontinuation of everolimus

b. Known adverse reactions to everolimus

-The most common grade -34 adverse events -(frequency $\geq 2\%$ in at least one pivotal study) were anemia, fatigue, diarrhea, infections, stomatitis, hyperglycemia, thrombocytopenia, lymphopenia, neutropenia, hypophosphatemia, hypercholesterolemia, diabetes mellitus, and pneumonitis. Grades follow the CTCAE version 4.0 classification.

Everolimus has immunosuppressive properties and may predispose patients to bacterial, fungal, viral or protozoal infections, including infections with opportunistic pathogens. Localized and systemic infections, including pneumonia, other bacterial infections, invasive fungal infections such as aspergillosis or candidiasis, and viral infections, including cases of hepatitis B reactivation, have been described in patients treated with everolimus. Some of these infections have been severe (e.g., leading to respiratory or hepatic failure), sometimes with fatal outcome.

Physicians and patients should be aware of the increased risk of infection with everolimus. Pre-existing infections should be treated before starting everolimus therapy. During treatment with everolimus, vigilance for signs and symptoms of infection should be exercised; if an infection is diagnosed, appropriate treatment should be initiated as soon as possible and temporary or permanent discontinuation of everolimus should be considered. If a diagnosis of invasive systemic fungal infection is made, everolimus must be discontinued and appropriate antifungal therapy initiated.

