Hypersensitivity reactions with symptoms including anaphylaxis, dyspnea, flushing, chest pain, or angioedema (e.g., swelling (edema) of the airways or tongue, with or without respiratory failure) have been observed with everolimus.

Hyperglycemia has been reported in clinical trials. It is recommended that fasting blood glucose be monitored prior to initiation of everolimus therapy and periodically thereafter. Optimal glycemic control should be achieved prior to initiating everolimus therapy in a patient. Mouth ulcers, stomatitis and oral mucositis have been observed in patients treated with everolimus. In these cases, topical treatments are recommended, but alcohol or hydrogen peroxide mouthwashes should be avoided.

Elevations in serum creatinine, usually mild, have been reported in clinical trials. It is recommended that renal function be monitored before starting everolimus therapy and periodically thereafter.

Decreases in hemoglobin, lymphocytes, platelets and neutrophils have been reported in clinical

trials. It is recommended that complete blood counts be monitored prior to the initiation of everolimus therapy and periodically thereafter.

The use of live vaccines and close contact with individuals who have received live vaccines should be avoided during treatment with everolimus.

Hypophosphatemia, hypomagnesemia, hyponatremia and hypocalcemia have been reported.

c. Management of stomatitis/oral mucositis/aphthae

Oral stomatitis/mucositis/ mouth ulcers due to everolimus should be treated with local symptomatic therapy. It should be noted that investigators in previous trials have described oral toxicities associated with everolimus in terms of mouth ulcers rather than mucositis or stomatitis. If your examination reveals canker sores rather than more general inflammation of the mouth, please classify the adverse event as such. Please follow the template below for treatment of oral stomatitis/mucitis/aphthas:

1. For mild toxicity (Grade 1), use conservative measures such as **alcohol-free mouthwash or salt water mouthwash (0.9%)** several times a day until resolved.

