- Clinical assessment: weight, general condition (WHO)
- Evaluation of the tolerance of the previous embolization or chemoembolization
- Biological check-up:
 - CBC-platelets
 - INR, aPTT, creatinine, bilirubin (total, conjugated), AST, ALT, PAL

NB: An abdominal CT scan may be performed if necessary for technical reasons before the 2nd embolization or chemoembolization session. Caution: this imaging should not be used to evaluate the response to treatment of metastases.

Every 3 months (+/- 1 week) from the date of the first embolization or chemoembolization (except DNA and ARC monitoring for positive serology)

- Clinical assessment: WHO, weight, evaluation of side effects
- Bioassay:
 - CBC/platelets, urea and creatinine + calculated creatinine clearance (Cockcroft formula), blood ionogram
 - INR, aPTT, albumin, alkaline phosphatase, AST, ALT, bilirubin (total and conjugated), gamma-GT
 - Serum cholesterol and triglycerides
 - Fasting blood glucose and HbA1c
 - Chromogranin A, urinary 5HIAA
- If HBV positive, monitor DNA approximately every 3 weeks or 6 weeks depending on the result (see Table 2-2)

- If HCV positive, monitor RNA every 6 weeks (see Table 2.3)
- Morphological assessment: triphasic thoracic-abdominal-pelvic CT scan with target measurement according to RECIST V1.1 criteria (Appendix 3). Evaluation CT scans should be performed in the same center as the initial examination

NOTE: Patients whose treatment is temporarily or permanently discontinued due to an adverse event or laboratory abnormality suspected to be related to everolimus should be monitored at least weekly until the adverse event resolves or returns to Grade 1

2. Post-treatment monitoring protocol

- **After discontinuation of treatment for hepatic progression**
 - After hepatic progression, the clinical, biological and morphological monitoring of the patient will be left to the investigator's discretion
- **After discontinuation of treatment for a reason other than hepatic progression**
(e.g. toxicity, extra-hepatic progression, patient's wish, :)
 - Morphological surveillance: CT every 3 months until liver progression occurs, according to the same modalities as the initial morphological evaluation (triphasic thoraco-abdomino-pelvic CT with target measurement according to RECIST V1.1 annex 3)

IX. STOP PROCESSING THE STUDY

The processing of the study will be stopped in case of:

- Investigator's decision

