7.6.4 Toxicities

Population SP

Toxicities (graded according to NCI-CTC v 4.0) will be described by:

- The total number of patients by maximum grade of toxicity (grade 1-2-3-4-5);
- The number of patients and the maximum toxicity grade achieved (grade 1-2-3-4-5) by SOC and type of toxicity;
- Total number of patients by maximum grade of toxicity by grouping grades (grade 1-2 and grade 3-4-5);
- The number of patients and the maximum grade of toxicities achieved by grouping the grades (grade 1-2 and grade 3-4-5) by SOC and type of toxicities.

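### SAP 7.6.4 plans no grouped row for oral toxicity, so if sites use more than one label each row may understate it and the patient-level incidence cannot be recovered

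*Protocol*

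**What the plan says.** **Oral toxicity.** Protocol VII.2.b gives the most common grade 3-4 events, meaning those that reached 2% in one or more pivotal studies: "anemia, fatigue, diarrhea, infections, stomatitis, hyperglycemia, thrombocytopenia, lymphopenia, neutropenia, hypophosphatemia, hypercholesterolemia, diabetes mellitus, and pneumonitis". Section VII.2.c puts stomatitis, oral mucositis and aphthae under one heading with one grade-based management scheme. It notes that "investigators in previous trials have described oral toxicities associated with everolimus in terms of mouth ulcers rather than mucositis or stomatitis", and then instructs sites: "If your examination reveals canker sores rather than more general inflammation of the mouth, please classify the adverse event as such".

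SAP 7.6.4, run in the safety population, asks for a count by maximum grade over all toxicities and for "The number of patients and the maximum toxicity grade achieved (grade 1-2-3-4-5) by SOC and type of toxicity". Both are repeated with grades grouped, the first as "Total number of patients by maximum grade of toxicity by grouping grades (grade 1-2 and grade 3-4-5"). No row combines the oral labels.

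**Electrolytes.** Hypophosphatemia is on the VII.2.b list, and the same section adds: "Hypophosphatemia, hypomagnesemia, hyponatremia and hypocalcemia have been reported". The three-monthly panel in Protocol VIII.1 begins "CBC/platelets, urea and creatinine + calculated creatinine clearance (Cockcroft formula), blood ionogram" and goes on to liver tests, lipids, glucose and tumour markers. Phosphate, magnesium and calcium are not named there, in the examination schedule, in the inclusion assessment (III) or in the SAP baseline biology list (7.2.4). The contents of the ionogram are not defined.

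**The concern.** The protocol treats the three oral conditions as one toxicity for management but asks for them to be recorded under different labels. It also knows that labelling has varied in earlier trials. A table that stops at SOC and type would then spread one toxicity over several rows. No single row gives its frequency. Adding rows counts twice any patient who had two labels, and the SOC row includes unrelated events.

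For the electrolytes the question is whether a low count means that the event was rare or that nobody looked.

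Tolerance over 24 months is a stated secondary objective (Protocol I.2, SAP 3.2.2). The trial has one arm, so there is no control group in which the same labelling or under-ascertainment would show up.

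**Working it through.** **Inputs.** The documents give no rate for oral toxicity or hypophosphatemia in this trial, so all event counts below are assumed. The denominator is the largest possible safety population. SAP 6.1.2 defines that population as included patients who took any everolimus, so it cannot exceed the 72 planned. The 72 reproduces from SAP 5.5: 68 / (1 - 0.05) = 71.6, rounded up to 72. The figure of 68 is the evaluable number for the primary endpoint and is not the right denominator here.

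**Oral rows.** Let two labels have a and b patients among n. The number with either label lies between max(a, b), if the same patients carry both, and a + b, if no patient does (as long as a + b does not exceed n).

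With a = b = 4 and n = 72:
- lower bound 4/72 = 5.6% (exact 95% CI 1.5 to 13.6%)
- upper bound 8/72 = 11.1% (exact 95% CI 4.9 to 20.7%)

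The two planned rows are identical in both cases, so a reader cannot tell them apart.

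The other way round, suppose each affected patient carries one label and the labels are used evenly:

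| Patients with any oral event | Grouped row | Each row, two labels | Largest row, three labels |
|---|---|---|---|
| 4 | 5.6% | 2/72 = 2.8% | 2/72 = 2.8% |
| 6 | 8.3% | 3/72 = 4.2% | 2/72 = 2.8% |
| 8 | 11.1% | 4/72 = 5.6% | 3/72 = 4.2% |
| 12 | 16.7% | 6/72 = 8.3% | 4/72 = 5.6% |

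If every site uses one label, the type row equals the grouped row and nothing is lost.

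**Other rows of SAP 7.6.4.** The overall maximum-grade row does not depend on labels, but it says nothing specific about the mouth. An SOC row that holds all the oral labels counts each patient once, but mixes them with other events, such as diarrhea, which is also on the VII.2.b list.

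**Electrolytes.** Assume that patients without a phosphate value stay in the denominator with no event, and that testing is unrelated to risk. Then shown % = true % x share measured. For an assumed true rate of 10%:
- 10% measured: 0.10 x 10% = 1.0%
- 25% measured: 2.5%
- 50% measured: 5.0%
- 75% measured: 7.5%
- 100% measured: 10%, with no understatement

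The documents do not fix the share measured, so the dilution could be anything from none to nearly total.

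**The case against.** **On the oral rows.** SAP 7.6.4 does not define type of toxicity, and the case report form and toxicity appendix are not available, so coding could yet merge the labels. Distinguishing canker sores from general inflammation is a deliberate request, and rows that report what was asked for are accurate in themselves. Label-free rows exist too: the overall maximum grade and, with mixing, the SOC. All of this stands, and it makes the understatement conditional. It does not remove the gap, because neither document says that the labels will be merged and no planned row gives a patient-level oral incidence.

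**On the electrolytes.** A reader might infer that hypophosphatemia will go unmeasured and be shown as absent in all treated patients, with a tight interval around zero. The documents do not support that:
- The ionogram is not itemised and may include phosphate.
- Protocol XI has all adverse events recorded, so a low value found locally and judged an adverse event would be captured.
- SAP 7.1.7 leaves missing values out of percentages, though it does not say whether a never-measured analyte is missing or counts as no event.
- SAP 7.6.4 asks for numbers of patients and states no percentage denominator or interval.

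Nor do the panels contradict the list of reactions. VII.2.b recommends monitoring of glucose, renal function and blood counts, and makes no such recommendation for phosphate, magnesium or calcium. What remains is a request for clear reporting.

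**Conclusion.** The oral point holds as a gap in the tables. If more than one label is used, single rows may understate oral toxicity and the combined incidence cannot be recovered. In the two-label illustration the uncertainty is a factor of two, 5.6% to 11.1%. The counts behind it are assumed, and the effect disappears if sites or coders use one label.

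The electrolyte point is secondary. It rests on an undefined term, and its size cannot be set from the documents.

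A reader might conclude that the tables will make the combination look better tolerated than it is. That goes too far: the plan does not prevent understatement, but nothing in it shows that understatement will occur. The 2% in VII.2.b is a criterion met in at least one pivotal study and is not a lower bound for this population. The primary endpoint and its decision rule of 31 of 68 are untouched. Dose changes, interruptions, permanent stops and serious adverse events are described separately. This is a minor improvement worth making.

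**What to change.** SAP 7.1.2 allows adjustments before the database is frozen. Within that window:

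1. In SAP 7.6.4, add one pre-specified grouped row, stomatitis/oral mucositis/aphthae. Count each patient once, at the maximum grade over the labels, and keep the separate label rows beside it. List the terms that feed the group.
2. State which analytes the blood ionogram covers. For hypophosphatemia, hypomagnesemia and hypocalcemia, report the number of safety-population patients with at least one on-treatment value beside the event count. If none was measured, write that the toxicity was not systematically assessed.

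The cost is one table row, a few lines of SAP wording and a count of patients with values. The grouped oral figure may be less favourable than any single row. No change to the tests done or to clinical management is asked for.

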Grade 2 (except pneumonia - see Table 1-4)	If toxicity is tolerable to the patient, maintain the same dose. In case of intolerable toxicity for the patient, discontinue everolimus until recovery to grade ≤ 1 . Then reintroduce everolimus at the same dose. If an event returns to grade 2, discontinue everolimus until recovery to grade ≤ 1 . Then reintroduce everolimus at the lower dose level.
Grade 3 (except hyperlipidemia*) (except pneumonia - see Table 1-4)	Interrupt everolimus until recovery to grade ≤ 1 . Then reintroduce everolimus at the lower dose level. For pneumonia, consider short-term steroid therapy.
Grade 4	Stopping everolimus
Any non-hematologic toxicity requiring interruption for a period ≥ 3 weeks	Stopping everolimus

*Grade 3 hyperlipidemia (hypercholesterolemia and/or hypertriglyceridemia) should be managed with medical treatments.

Table 1-2

HEMATOLOGICAL Toxicity (NCI-CTC V4.0)	Grade	Actions
Thrombocytopenia	Grade 2 (platelets $< 75, \geq 50 \times 10^9 /l$)	Interrupt everolimus until recovery to grade ≤ 1 ($\geq 75 \times 10^9 /l$). Then reintroduce everolimus at the initial dose. If thrombocytopenia returns to grade 2, discontinue everolimus until recovery to grade ≤ 1 . Then reintroduce everolimus at the lower dose level.
	Grade 3 (platelets $< 50, \geq 25 \times 10^9 /l$)	Interrupt everolimus until recovery to grade ≤ 1 (platelets $\geq 75 \times 10^9 /l$). Then resume everolimus at a lower dose level.

		If thrombocytopenia recurs at grade 2, discontinue everolimus.
	Grade 4 (platelets < 25×10^9 /L)	Stopping everolimus
Neutropenia	Grade 3 (neutrophils < 1, $\geq 0.5 \times 10^9$ /L)	Interrupt everolimus until recovery to grade ≤ 1 (neutrophils $\geq 1.5 \times 10^9$ /L). Then resume everolimus at the initial dose. If PNN returns to grade 3, withhold everolimus until PNN is $\geq 1.5 \times 10^9$ /L. Then resume everolimus at the lower dose level. Discontinue study treatment if a third episode of Grade 3 neutropenia occurs
	Grade 4 (neutrophils < 0.5×10^9 /L)	Interrupt everolimus until recovery to grade ≤ 1 (neutrophils $\geq 1.5 \times 10^9$ /L). Then resume everolimus at the lower dose level. If Grade 3 or 4 neutropenia occurs despite this dose reduction, discontinue everolimus

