2. For more severe toxicity (grade 2, in which case patients are able, despite pain, to maintain adequate oral nutrition, or grade 3 in which case patients cannot maintain adequate oral nutrition), the proposed treatments are **analgesic topical oral treatments (i.e., local anesthetics such as benzocaine, butylaminobenzoate, tetracaine hydrochloride, menthol, or phenol)** with or without **topical corticosteroids**, such as triamcinolone acetonide 0.1% gingival paste (Orabase Kenalog®).
3. Agents containing hydrogen peroxide, iodine and thyme derivatives may tend to exacerbate mouth ulcers. It is best to avoid these agents.
4. Antifungal agents should be avoided unless a fungal infection has been diagnosed. In particular, systemic imidazole antifungal agents (ketoconazole, fluconazole, itraconazole, etc.) should be avoided in all patients as they are potent inhibitors of everolimus metabolism, resulting in higher everolimus exposures. Therefore, topical antifungal agents are preferable if an infection is diagnosed. Similarly, antiviral agents such as acyclovir should be avoided unless a viral infection is diagnosed.

d. Management of hyperlipidemia and hyperglycemia

Hyperlipidemia and hypertriglyceridemia should be treated according to local best clinical practice.

e. Management of non-infectious lung disease

Non-infectious pneumonitis is a class effect of rapamycin derivatives. Non-infectious lung disease (including interstitial lung disease) has also been described in patients treated with everolimus. A diagnosis of non-infectious lung disease should be considered in patients presenting with non-specific respiratory signs and symptoms such as cough or dyspnoea, hypoxia, pleural effusion, and when infectious, neoplastic or other non-drug causes have been excluded by appropriate investigations. Patients should be asked to report promptly any new or worsening respiratory symptoms.

Patients with radiological changes suggestive of non-infectious lung disease with few or no symptoms may continue everolimus therapy without a change in dosage. In the presence of moderate symptoms (Grade 2), discontinuation of treatment should be considered until symptoms improve. Administration of corticosteroids may be indicated. Everolimus may be reintroduced at a reduced dose until recovery to Grade 1 or higher.

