When symptoms of non-infectious lung disease are severe (Grade 3), everolimus treatment should be discontinued and corticosteroids may be indicated until clinical symptoms resolve. Everolimus treatment may be reintroduced at a reduced dose depending on individual clinical circumstances.

Table 1-4Management of non-infectious lung disease

PNEUMOPATHY (NCI-CT V 4.0)	INVESTIGATION REQUIRED	CARE	EVEROLIMUS DOSE ADJUSTMENT
Grade 1	Chest CT in the lung window and respiratory function tests, including spirometry, DLCO, and room air O ₂ saturation at rest. Repeat chest x-ray/computed tomography every 2 cycles until normal.	No specific treatment is required	Administer 100% of the everolimus dose.
Grade 2	Chest CT in lung windows and pulmonary function tests, including spirometry, DLCO, and room air O ₂ saturation at rest. Repeat with each subsequent cycle until normalcy is achieved.	Symptomatic only. Prescribe corticosteroids if cough is troublesome.	Reduce everolimus dose until recovery to a grade \leq 1. Everolimus may also be discontinued if troublesome symptoms occur. Patients will discontinue treatment if they fail to recover to a grade \leq 1 within 3 weeks
Grade 3	Bronchoscopy is recommended *	Prescribe corticosteroids if an infectious origin is excluded. Gradually reduce the dose according to medical indication.	Withhold treatment until recovery to a grade \leq 1. The treatment protocol may be restarted within 2 weeks at a reduced dose (by one level) if there is evidence of clinical benefit. Patients will discontinue treatment if they fail to recover to a grade \leq 1 within 2 weeks.
Grade 4		Prescribe corticosteroids if an infectious origin is excluded. Gradually reduce the dose according to medical indication.	Stop the treatment.

*Bronchoscopy with biopsy and/or bronchoalveolar lavage is recommended.

f. Management of reactivation /flare-up of hepatitis

In cancer patients with hepatitis B virus, either carrier or chronic, the administration of antivirals during cancer therapy has been shown to reduce the risk of hepatitis B virus (HBV) reactivation and associated morbidity and mortality (Loomba et al. 2008).

- **Monitoring and prophylaxis for hepatitis B reactivation**

Table 2-1 provides detailed information on monitoring and prophylactic treatment based on initial viral load and serologic marker test results.

Table 2-1: Actions to be Taken for Initial Positive Hepatitis B Results

Test	Result	Result	Result	Result	Result
HBV DNA	+	+ or -.	-	-	-

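### The pneumonitis text in Protocol VII.2.e gives the grade 2 recovery threshold in the wrong direction and leaves out stopping and restart limits that Table 1-4 sets

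*Protocol*

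**What the plan says.** Protocol VII.2.e covers non-infectious lung disease twice, first in running text and then in Table 1-4.

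- **Grade 2, text.** Interruption is to be considered until symptoms improve. Then: "Everolimus may be reintroduced at a reduced dose until recovery to Grade 1 or higher". No time limit is given.
- **Grade 2, Table 1-4.** "Reduce everolimus dose until recovery to a grade" of 1 or below. Interruption is optional: "Everolimus may also be discontinued if troublesome symptoms occur". There is a stop: "Patients will discontinue treatment if they fail to recover to a grade" of 1 or below within 3 weeks.
- **Grade 3, text.** "everolimus treatment should be discontinued and corticosteroids may be indicated until clinical symptoms resolve". Then: "Everolimus treatment may be reintroduced at a reduced dose depending on individual clinical circumstances".
- **Grade 3, Table 1-4.** Treatment is withheld until grade 1 or below. Then: "The treatment protocol may be restarted within 2 weeks at a reduced dose (by one level) if there is evidence of clinical benefit". Treatment ends if grade 1 or below is not reached within 2 weeks.

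Three other provisions bear on this. VII.2 says that the dose-adjustment rules are defined in Tables 1.1 and 1.2, and it takes a patient out of the study if treatment is delayed by more than 21 days. Table 1-1 refers pneumonia elsewhere, in the row labelled "Grade 2 (except pneumonia - see Table 1-4" and in the same way for grade 3. A further row of Table 1-1 stops everolimus after any non-hematological interruption of 3 weeks or more.

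**The concern.** Two sets of dosing instructions for the same toxicity stand side by side and do not agree. At grade 2 the text points the wrong way. Read literally, a patient at grade 2 or grade 3 already satisfies its condition, so it sets no recovery target. At grade 3 the text gives the investigator discretion where the table sets conditions and a stop.

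A site working from the text alone could keep a grade 2 patient on reduced-dose everolimus beyond 3 weeks, or restart a grade 3 patient whom the table requires to stop. VII.2.e itself calls pneumonitis a class effect of rapamycin derivatives, and VII.2.b lists it among the common grade 3-4 events, so the instruction is likely to be used. What is at stake is patient safety and consistent dosing across centres.

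**Working it through.** The plan states no figure to reproduce, and the documents give no pneumonitis rate for this population. The check is a comparison of text and table, with one small piece of arithmetic for grade 3.

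| Item | Text of VII.2.e | Table 1-4 | Result |
|---|---|---|---|
| Grade 2: recovery threshold | grade 1 or above | grade 1 or below | contradiction |
| Grade 2: time limit | none | stop at 3 weeks | omitted |
| Grade 3: recovery needed | symptoms resolving, no grade | grade 1 or below | stated loosely |
| Grade 3: dose at restart | reduced, size not given | one level lower | stated loosely |
| Grade 3: time limit | none | 2 weeks, otherwise stop | omitted |
| Grade 3: clinical benefit | not mentioned | evidence required | omitted |

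**Do the general limits fill the grade 2 gap?** The text only asks that interruption be considered, and the table makes it optional, so a grade 2 patient may stay on drug without a break.

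- The VII.2 limit needs a delay, and the Table 1-1 row needs an interruption. Neither is triggered by continuous dosing at a reduced level.
- The weekly monitoring rule in VII.2 and VIII.1 covers patients whose treatment has been temporarily or permanently stopped, so it does not reach this patient either.
- The 3-week stop in Table 1-4 is therefore the explicit time limit that applies, and the text lacks it.

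**How far apart are text and table on grade 3 timing?** Here treatment is interrupted, so the general limits do apply. Count the first missed dose as day 0.

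- Table 1-4 allows recovery up to day 14 (2 weeks).
- Table 1-1 stops at an interruption of 21 days or more, so the last permitted day is 20. The gap is days 15 to 20: 20 − 14 = 6 days.
- VII.2 acts on a delay of more than 21 days, so the last permitted day is 21. The gap is days 15 to 21: 21 − 14 = 7 days.

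On timing alone, then, the two disagree only for a grade 3 patient who recovers in that 6- or 7-day window. The missing clinical-benefit condition and the missing recovery grade are not confined to that window.

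**The case against.** The strongest reply is that precedence is already settled. VII.2 places the adjustment rules in tables, Table 1-1 sends grade 2 and grade 3 pneumonia to Table 1-4, and Table 1-4 directly follows the text and has its own dose-adjustment column. This largely stands, and it is why the impact is small. It is not a full cure. VII.2 names Tables 1.1 and 1.2 and not Table 1-4, and VII.2.e never says which version prevails.

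Second, the wrong direction may be a translation error. The document reads as a rough translation from French, and the French text cannot be checked here. That is fair. The sentence is still wrong in the protocol as supplied.

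Third, if the grade 2 sentence is read as meaning reintroduction *after* recovery, the Table 1-1 stop at 3 weeks matches Table 1-4 for an interrupted patient. That also stands, but it leaves out the patient who is never interrupted.

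Fourth, a reader might infer that the grade 3 text omits all four of the table's restart conditions. It does not: it mentions a reduced dose and resolution of symptoms. Only the 2-week limit and the clinical-benefit condition are wholly absent.

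**Conclusion.** The point holds as a minor inconsistency in safety instructions. One element is a contradiction (the grade 2 threshold). Three are omissions from the text (the 3-week stop at grade 2, and the 2-week limit and clinical-benefit condition at grade 3). Two are loose statements (recovery grade and size of the dose reduction at grade 3).

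Three stronger readings are tempting and not supported:

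- **That the protocol has no stopping rule for pneumonitis.** Table 1-4 contains one for each of grades 2 and 3.
- **That giving a reduced dose during grade 2 is itself an error.** Table 1-4 permits it for up to 3 weeks.
- **That the trial's conclusion is at risk.** The sample size, the error rates and the rule of 31 or more successes among 68 evaluable patients do not depend on these sentences.

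The conclusion assumes that Table 1-4 states the sponsor's intended rule and that the translated wording is what sites would act on. How many patients would be affected cannot be estimated from the documents.

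**What to change.** Make three changes in VII.2.e.

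1. Add a sentence saying that Table 1-4 governs dose reduction, restart and stopping.
2. Replace the grade 2 sentence with: *Reduce the dose until recovery to grade ≤ 1; if everolimus was interrupted, reintroduce it at a reduced dose after recovery to grade ≤ 1; stop if grade ≤ 1 is not reached within 3 weeks.*
3. Replace the grade 3 reintroduction sentence with: *Everolimus may be restarted one dose level lower only if recovery to grade ≤ 1 occurs within 2 weeks and there is evidence of clinical benefit; otherwise stop.*

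Changing only the one wrong word at grade 2 would not be enough. The sentence would then allow an interrupted patient to restart before recovery, which Table 1-4 does not state. The sponsor should also check the French text and confirm that stopping here means permanently.

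The cost is one added sentence and two replaced ones, sent to sites as a clarification. No patients, visits or analyses are added.
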